5. ANALYSIS POPULATIONS

5.1 Enrolled Population

Enrolled Population includes all subjects with a signed informed consent form.

5.2 Safety Population

Safety Population includes all randomized subjects who use at least one dose of investigational drug (Reproxalap Ophthalmic Solution or Vehicle Ophthalmic Solution), regardless of whether clinical trial assessments were performed.

5.3 Intent-to-Treat (ITT) Population

ITT Population includes all randomized subjects who use at least one dose of investigational drug and have any post-dose assessments. Subjects are evaluated according to the investigational drug treatment of the visit as per the randomized treatment sequence.

5.4 Completer Population

Completer population will include all randomized subjects who received investigational drug dosing at all two EEC treatment visits.

[figure not shown]
5.5 Per-Protocol (PP) Population

Per-Protocol Population includes all subjects in Completer Population without a major deviation from the protocol.

5.6 Application of Analysis Population

Unless otherwise noted, the analysis populations that will be used for creating the summary tables of each type is provided in [Table 2](#).

Table 2. Application of Populations on Tables

6. STATISTICAL CONSIDERATIONS

All analyses described in this plan are considered a priori analyses in that they have been defined prior to locking the database. All other analyses, if any, designed subsequently to locking the database, will be considered post hoc analyses and will be described as exploratory analyses in the Clinical Study Report.

All summaries and statistical analysis will be performed [REDACTED].

6.1 General Statistical Procedures

Frequency distributions for categorical variables will be provided as number of patients in the category and the percentages of the total number of patients in the given population as noted. Percentages will be reported to one decimal place.

The descriptive statistics for continuous variables will be number of subjects (n), mean, standard deviation (SD), median, minimum and maximum. Mean and median will be reported to 1 more decimal place than the raw data, while the SD will be reported to 2 more decimal places than the raw data. Minimum and maximum will be reported the same as the original data.

All statistical tests will be two-sided with a significance level of 0.05 ($\alpha = 0.05$) unless otherwise specified. Confidence interval (CI) for differences between treatment will be two-sided at 95% confidence interval.

P-value will be rounded to at most 3 decimal places and will be reported as < 0.001 if it is smaller than 0.001.

Unless otherwise specified, subjects' characteristics at baseline will be summarized by treatment sequences (Reproxalap 0.25%/Vehicle, Vehicle/Reproxalap 0.25%). Safety and efficacy will be summarized by treatment (Reproxalap 0.25%, Vehicle) where appropriate.

In general, all listings will be ordered by subject number and visit for available data unless otherwise specified in the text.

6.2 Subject Disposition

Frequency and percentage of subject disposition will be summarized by treatment sequence and all subjects for Enrolled Population including:

- Number of subjects with screen failure
- Number of subjects randomized
- Number of subjects in each analysis population
- Number of subjects who completed each treatment
 - Reproxalap Ophthalmic Solution 0.25%
 - Vehicle Ophthalmic Solution
- Number of subjects only completed first treatment session

Percentage will be based on number of subjects randomized.

Study discontinuation will be summarized by treatment for Safety Population including:

- Number of subjects discontinued from study
- Reasons for study discontinuation

- Subject request/withdrawal
- Adverse event
- Pregnancy
- Protocol violations
- Administrative reasons
- Sponsor termination
- Any sound medical reason
- Other

Percentage is based on number of subjects in Safety Population.

Subjects' disposition will be listed for Enrolled Population. In addition, subjects excluded from study will be listed for Enrolled Population.

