**Visit 3 Post-EEC exit (starting at approximately t = 215 minutes):**

- 1) Subject assessed ocular itching and tearing will continue [REDACTED]  
[REDACTED];
- 2) Staff assessed conjunctival redness will continue to be recorded post-EEC exit [REDACTED]  
[REDACTED].

Subjects will be asked to return in at least two weeks for Visit 4.

At the **Treatment EEC Session Two (Visit 4)**, all procedures performed at Visit 3 will be repeated except that each subject will be given a different treatment dependent on the treatment sequence the subject was randomized to [Reproxalap Ophthalmic Solution (0.25%) (Treatment A) or Vehicle Ophthalmic Solution (Treatment B)].

Before EEC entry, a urine pregnancy test will be administered to WOCBP.

Subjects will undergo ophthalmic examinations (Snellen VA, SLE, NCT, and a dilated fundus examination), clinical safety lab tests and vital signs will be collected to ensure safety prior to exit of the clinical trial.

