### 5.2 Discontinued Subjects

Subjects may be discontinued prior to their completion of the clinical trial due to:

- Subject request/withdrawal;
- AEs;
- Positive COVID-19 test result;
- Positive pregnancy results;
- Protocol violations;
- Administrative reasons (e.g., inability to continue, lost to follow-up);
- Sponsor termination of the clinical trial;
- Any sound medical reason, as determined by the investigator; or
- Other.

Notification of a subject discontinuation and the reason for discontinuation will be made to the Sponsor or designee and will be clearly documented on the eCRF. Subjects who are discontinued from the clinical trial will not be replaced.

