## **7.8.4 COVID-19 Test (SARS-CoV-2 PCR)**

Within 5 days of study visits 2, 3, and 4 a nasopharyngeal or oropharyngeal swab will be collected at the clinical site for SARS-CoV-2 PCR testing. Subjects with a positive test result will be excluded/withdrawn from the study.

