### 8.1 COVID-19 Screening

The following procedures will be performed as part of COVID-19 screening:

- Subjects will be pre-screened based upon a COVID-19 questionnaire at each visit;
- Body temperature will be measured at each visit. This measurement may be in addition to other vitals taken at the visit;
- A nasopharyngeal/oropharyngeal swab will be collected for COVID-19 testing within 5 days prior to each EEC session (Visits 2, 3, and 4).
- Most recent COVID-19 test result [REDACTED] will be reviewed prior to entering the EEC at Visits 2, 3, and 4. Subjects will be allowed to enter the EEC only if COVID-19 test result is negative.

Subject's further participation in the study will be based on the results of the COVID-19 test results and procedures.

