## **10.5 Accountability and Background Characteristics**

### **10.5.1 Enrollment and Disposition**

The number of subjects enrolled, by study population and investigative site, will be presented by treatment group. The primary reasons for discontinuation will be summarized by treatment and based on the safety population. The number and percentage of subjects with protocol deviations or subjects requiring rescue therapy leading to exclusion from the PP population will be presented by reason for exclusion, stratified by treatment. All deviations and rescued subjects will be listed.

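### Does SAP 6.2 need a rule for which treatment is charged with a discontinuation between the two chamber sessions?

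*SAP*

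**What the plan says.** SAP 6.2 has two displays. The first gives disposition by treatment sequence, with percentages of those randomized, and includes this line: "Number of subjects only completed first treatment session". The second is the one at issue: "Study discontinuation will be summarized by treatment for Safety Population including" the number discontinued and the reasons. Its denominator is given: "Percentage is based on number of subjects in Safety Population". Subject-level disposition is also listed. Protocol 10.5.1 agrees with the second display: "The primary reasons for discontinuation will be summarized by treatment and based on the safety population".

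SAP 6.4 tabulates deviations by treatment for the Safety Population and lists all of them. SAP 6.1 sets the general rule that percentages use the total of the stated population. SAP 5.2 defines the Safety Population by use of at least one dose of either product.

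SAP 7.2 holds the only rule for the interval between sessions. Treatment-emergent adverse events that start before the Visit 4 dosing date count to the Visit 3 session. The rule is written for adverse events only.

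On reasons for leaving, Protocol 5.2 lists "Positive COVID-19 test result". The SAP 6.2 list does not, but it ends with a catch-all category.

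**The concern.** A subject who completes both sessions appears under reproxalap and under vehicle, whereas a discontinuation happens once. If it happens after Visit 3 and before Visit 4 dosing, SAP 6.2 does not say which column receives it.

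The protocol makes such exits likely. Protocol 3.1 states: "Subjects will be asked to return in at least two weeks for Visit 4". The COVID-19 swab for Visit 4 is taken within the 5 days before that visit, and Protocol 7.8.4 adds: "Subjects with a positive test result will be excluded/withdrawn from the study". A pregnancy test also precedes Visit 4, and a pregnancy means withdrawal.

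Three things seem to be at stake. Safety is part of the primary objective, and discontinuation by product is one of its displays. If the two sequences lose different numbers, the assignment rule could decide which product shows more discontinuations. And a subject who stops for an adverse event between sessions falls under the Visit 3 product in the SAP 7.2 table of events leading to discontinuation, but could fall under the other product in SAP 6.2, so the two tables might disagree.

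The denominator also looks open. The Safety Population total could mean everyone dosed, or only those dosed with the product in that column.

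**Working it through.** The plan states no figure for this point, so there is none to reproduce. The arithmetic below shows only how large the effect could be.

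**Inputs.** About 126 randomized, about 63 per sequence, and 100 completing (Protocol 10.3; SAP 2.2).

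**Assumptions.** All 126 are dosed at Visit 3, and every non-completer leaves before Visit 4 dosing. Then d = 126 − 100 = 26 leavers. This is a planning figure; the number would be larger if fewer than 100 completed.

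**Timing.** Visit 4 is at least 14 days after Visit 3 and the swab is at most 5 days before Visit 4. The swab is therefore taken at least 14 − 5 = 9 days after Visit 3 dosing, inside the interval.

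**Notation.** Let a be the leavers from sequence AB (reproxalap only received) and b those from BA (vehicle only received). Dosed with reproxalap: 126 − b. Dosed with vehicle: 126 − a.

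**Denominator, equal loss.**

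| a / b | Whole Safety Population | Dosed with that product |
|---|---|---|
| 13 / 13 | 13/126 = 10.3% | 13/113 = 11.5% |
| 3 / 3 | 3/126 = 2.4% | 3/123 = 2.4% |

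The two products show equal percentages on either base, so the comparison does not move.

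**Assignment, unequal loss (hypothetical a = 15, b = 11).**

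| Rule | Base | Reproxalap | Vehicle |
|---|---|---|---|
| Product received | 126 | 15/126 = 11.9% | 11/126 = 8.7% |
| Product received | dosed | 15/115 = 13.0% | 11/111 = 9.9% |
| Product missed | 126 | 11/126 = 8.7% | 15/126 = 11.9% |

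The direction changes only in the last row. There the reproxalap column counts 11 BA subjects who never had reproxalap. On the dosed base that count makes no sense, because those 11 are outside the denominator of 115. So the reversal needs two choices together: charging the product not received, and dividing by the whole population. If columns use subjects dosed, the reversal disappears; if columns use 126, the denominator question disappears. The two effects cannot both apply.

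**How ordinary is an uneven split?** If leaving is unrelated to sequence, a is hypergeometric (126 subjects, 63 in AB, d leavers). For d = 26 the SD is √(26 × 0.5 × 0.5 × 100/125) = 2.28, and a split at least as uneven as 15/11 has probability 0.51. For d = 13, 8/5 or worse has probability 0.56; for d = 6, 4/2 or worse has 0.68. Imbalance is to be expected, so the rule used does matter to the printed table.

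**What the plan already shows.** The by-sequence line for subjects with only the first session gives a and b almost directly. In the example it would read 15/63 = 23.8% for AB and 11/63 = 17.5% for BA. AB subjects with one session had reproxalap and BA subjects had vehicle, so a reader can see what the leavers received, whatever the by-treatment table does.

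**The case for a change.** The strongest case for a change is that the sponsor saw the need for an assignment rule in SAP 7.2 and wrote one, but did not extend it to SAP 6.2 and 6.4. Fixing the rule before database lock keeps it independent of results, costs a sentence, needs no new data and would keep the 6.2 and 7.2 tables in agreement. Read literally, SAP 6.1 and 6.2 put subjects never dosed with a product into that product's denominator. Some deviation categories in SAP 6.4, such as consent and eligibility, can arise before any dose and have no natural treatment column.

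Part of this stands. The assignment rule is absent, and the column N is not spelled out. But a denominator is stated, in SAP 6.2 directly and through SAP 6.1 for 6.4; what is open is only whether it is taken per product. Protocol 10.8, which reports adverse events per treatment group, fits the per-product reading. The possible disagreement between tables arises only if the programmer departs from the convention already in SAP 7.2, and nothing in the documents points that way. Deviations that precede dosing are listed by subject; where to tabulate them is a layout choice.

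The missing COVID-19 reason is a clerical slip. Protocol 5.2 requires the reason on the eCRF and the SAP list has a catch-all category, so no subject drops out of the table.

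**Conclusion.** No change to the plan is needed. This is a detail left open that analysts fill sensibly: they would count a between-session discontinuation under the Visit 3 product, as SAP 7.2 does for adverse events, and use subjects dosed with each product as the column N.

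Under that practice the tables are coherent. The remaining uncertainty is the size of the base, about 1.2 percentage points per column (11.5% − 10.3%) if 13 leave from each sequence, and nothing at one decimal place if 3 do. It is zero if every subject receives both products. No efficacy test or conclusion is touched, and the by-sequence counts and subject listings let a reader check the by-treatment display.

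This rests on reading discontinuation by the product received, for which SAP 7.2 is the only precedent in the documents, and on the planning figures of 126 and 100. The body of SAP Table 2 and the Appendix were not visible and may already settle the denominator.

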6.3 Extent of Study Drug Exposure

Exposure of study drug will be listed for Safety Population.

6.4 Protocol Deviations

Protocol deviations will be reviewed, assessed and documented by sponsor personnel before database lock.

Number and percentage of subjects with protocol deviation will be tabulated by treatment for Safety Population. The protocol deviations will be grouped into different categories which may include, but are not limited to:

- Missed visit
- Inclusion/Exclusion criteria
- Missed procedures/assessments
- Informed consent
- Documentation
- Study drug administration
- Safety
- Lack of compliance

All protocol deviations will be listed for Enrolled Population.

6.5 Demographic and Baseline Characteristics

Subjects' demographic and baseline characteristics will be summarized by treatment sequence and for all subjects including:

- Age at screening (years). If not reported, calculated as integer of (date of informed consent signed – date of birth)/365.25 and rounded to integer.
- Sex
- Race
- Ethnicity
- Height (cm)
- Weight (kg)
- BMI (body mass index, kg/m²), calculated as weight (kg) / height (m)²

Demographics and baseline characteristics will be listed for ITT Population.

6.6 Medical and Social History

Medical and social history will be coded using the Medical Dictionary for Regulatory Activities (MedDRA) [REDACTED]

The frequency count and percentage of patients experiencing any medical conditions will be tabulated by system organ classifications (SOC) and preferred term (PT) for each treatment. If a preferred term or system organ class was reported more than once for a subject, the subject would only be counted once in the incidence for that preferred term or system organ class.

Medical history data will be listed for ITT Population.

6.7 Prior and Concomitant Medications

All medications will be coded according to the WHO drug dictionary which includes the WHO Drug Preferred Name and the ATC Classification Level 2 and 4.

Prior medications are medications used 30 days prior to consent to treat any medical conditions and will be documented at medical screening visit.

Concomitant medications are medications being taken on or after first dose the study drug. Medications taken 30 days prior to informed consent date and were ongoing on the date of the first dose will be considered concomitant medications. Medications with missing end date are assumed to be concomitant medications.

Prior and concomitant medications will be listed ONLY for ITT Population.

7. Safety Analysis

7.1 Ophthalmic Examination Findings

Ophthalmic examination results will be summarized by anatomical location (eye) and side (left, right and both) at pre and post-EEC entry treatment sessions for Safety Population for following tests:

- Visual acuity measured using a Snellen eye chart
- Slit lamp examination (SLE)
- Non-contact intraocular pressure tonometry (NCT), measured using non-contact tonometry
- Fundoscopy including:
 - Dilated fundus examination at Visit 4
 - Undilated fundus examination at Visits 3

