**Statistical Analysis:**

Approximately 670 subjects with ragweed-induced, moderate-to-severe allergic conjunctivitis will be screened in order to randomize approximately 126 subjects, and for approximately 100 subjects to complete the study. Approximately sixty-three (63) subjects will be assigned to each of two (2) treatment sequences, AB and BA.

Prior to database lock, the Sponsor will finalize a statistical analysis plan (SAP) that will detail all planned analyses and will dominate any statistical analysis described herein. Any analyses conducted in addition to those specified in the SAP will be clearly documented as post hoc.

The efficacy analyses of all efficacy endpoints will be carried out in the Intent-to-Treat (ITT) population. Supportive analyses may also be provided for Itching endpoint(s) using the Per-Protocol (PP) population.

For the primary efficacy endpoint, Reproxalap Ophthalmic Solution (0.25%) will be compared to vehicle. Treatment comparisons at pre-specified time points (every 10 minutes from 110 to 210 minutes following chamber entry) will be performed by using a Mixed Model Repeated Measures (MMRM) approach for a crossover study with 2 periods.

Secondary efficacy endpoints will be analyzed by using a similar approach as the primary efficacy variable, except over the duration of the chamber (approximately 10 to 212 minutes), as assessed by a single p value for the treatment term. Further details of the analysis plan will be described in statistical analysis plan document (SAP).

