### **7.10.2 Slit Lamp Exam**

SLE observations will be graded as “normal” or “abnormal.” Abnormal findings will be categorized as clinically significant (findings that may interfere with trial parameters or otherwise confound the data as determined by the investigator) or not clinically significant. The cornea, conjunctiva, anterior chamber, lens, and eyelid will be examined.

SLE will be conducted at the Medical Screening Visit (Visit 1), and pre- and post-entry to the EEC at the Screening and Treatment EEC Sessions (Visits 2 through 4).

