### **7.10.3 Non-Contact Intraocular Pressure Tonometry (NCT)**

Intraocular pressure will be measured using non-contact tonometry. NCT will be measured at the Medical Screening Visit (Visit 1), prior to and post-EEC at the Treatment EEC Sessions (Visits 3 through 4).

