## **10.8 Safety Analysis**

Adverse events will be coded using the MedDRA dictionary.

Frequencies and percentages will be provided per treatment group of subjects with treatment-emergent adverse events (TEAEs), serious TEAEs, and TEAEs causing premature discontinuation. An adverse event is treatment-emergent if it occurs or worsens after the first dose of randomized study treatment. Furthermore, frequencies will be given of subjects with TEAEs by system organ class, by system organ class and preferred term, by system organ class, preferred term and maximal severity, by system organ class, preferred term and strongest relationship, and by system organ class, preferred term, maximal severity, and strongest relationship. Separate analyses will be performed for ocular specific and all adverse events (including systemic).

Other safety endpoints including visual acuity, slit lamp biomicroscopy, intraocular pressure (IOP), tear osmolarity and dilated fundoscopy will be summarized by treatment group and visit using descriptive statistics. Changes or shifts from baseline will also be summarized where appropriate. For assessments performed by eye, worst eye (study eye) and fellow eye will be summarized separately.

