4. DEFINITIONS AND CONVENTIONS FOR DATA HANDLING

4.1 Definition of Baseline

For Safety evaluations, baseline is defined as the last non-missing value measured prior to initiation of study drug.

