7.4 Vital Signs

Vital sign assessments will be taken with the subject in the sitting or supine position after 5 minutes at rest and will include body temperature, pulse rate, blood pressure (BP), and respiratory rate (RR) prior to EEC entry and at end of Visit 4 prior to study exit.

Observed and changes from baseline for vital signs will be summarized by visit. Baseline is defined as the last non-missing measurement taken prior to the first dose.

Listing will be provided for ITT Population.

8. Efficacy Analysis

The efficacy evaluation will be performed to assess the activity of Reproxalap Ophthalmic Solution based on the subjects reported ocular itching using a standard 9-point scale (0-4 scale with 0.5-unit increments) and tearing on a standard 4-point (0-3 scale) and trained staff assessed conjunctival redness using a standard 9-point scale (0-4 scale with 0.5 unit increments).

For all staff assessed and subject reported symptoms where values from both eyes are obtained at the same timepoint, the average score from both eyes will be used for analysis.

The following analysis will be performed for all efficacy endpoints using ITT Population:

- Observed and changes from baseline by visit and treatment
- Analysis using Mixed Model Repeated Measures (MMRM) using all available data collected during the EEC
- Plots for mean score over time, and mean changes of score from baseline over time

The onset of action time point and the duration of action will be reported for each efficacy endpoint whenever applicable. Duration of action will be the longest (in minutes) series of time points over which majority is statistically significant in favor of test drug, including the first and last time points in the series. Onset of action will be the first time point in the duration series. If two or more duration series are equivalent in length (in minutes), then the onset will be the first time point in the series that occurs earliest.

Subjects' assessment at Screening EEC and Post-EEC exit time points will be listed ONLY. All efficacy data will be listed for ITT Population.

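### SAP 7.1 summarizes visual acuity, slit lamp and eye pressure before and after each session separately and does not carry over the protocol's change or shift summaries, so non-AE worsening is not tabulated by product

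*SAP*

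**What the plan says.** SAP 7.1 covers VA, SLE, NCT and fundoscopy in one sentence: "Ophthalmic examination results will be summarized by anatomical location (eye) and side (left, right and both) at pre and post-EEC entry treatment sessions", in the Safety Population. Nothing in that section is blacked out. It mentions no change, no shift and no count of newly abnormal eyes.

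Four other places bear on this:

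- Protocol 10.8 names visual acuity, slit lamp and intraocular pressure among the other safety endpoints and adds: "Changes or shifts from baseline will also be summarized where appropriate".
- The statistical section of the protocol synopsis says that the SAP "will detail all planned analyses and will dominate any statistical analysis described herein". Protocol 10.3 says nearly the same.
- SAP 7.4 handles another safety measure differently: "Observed and changes from baseline for vital signs will be summarized by visit".
- SAP 4.1 gives one general rule: "For Safety evaluations, baseline is defined as the last non-missing value measured prior to initiation of study drug".

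On collection, Protocol 7.10.1 and 7.10.2 schedule VA and SLE before and after chamber entry at Visits 2 to 4. Protocol 7.10.3 schedules NCT before and after the chamber at Visits 3 and 4. SLE is graded normal or abnormal, and abnormal findings are classed as clinically significant or not.

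**The concern.** The product is an eye drop, and safety is part of the primary objective (Protocol 2.1, SAP 3.1). The crossover gives every completer a same-day before/after pair on each product. The informative question is how many eyes became abnormal, lost acuity or rose in pressure within a session, on reproxalap and on vehicle. SAP 7.1 as written produces two sets of separate summaries and leaves that question unanswered.

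The protocol did foresee the answer, but the plan for it did not reach the document that governs. If a programmer added a change from baseline later, SAP 4.1 would not say clearly which examination is the reference for Visit 4.

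This point is limited to VA, SLE and NCT. At the treatment sessions fundoscopy is scheduled only after the chamber (Protocol 7.10.4), so it has no same-session pair.

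**Working it through.** The documents state no figure on this point, so there is none to reproduce. The check compares the texts and then asks what separate columns can and cannot show.

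**1. What is planned, side by side**

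| Measure | Pre/post in each treatment session | Change or shift in protocol | Change or shift in SAP |
|---|---|---|---|
| VA | yes (Protocol 7.10.1) | yes, where appropriate (10.8) | not named (7.1) |
| SLE | yes (Protocol 7.10.2) | yes, where appropriate (10.8) | not named (7.1) |
| NCT | yes (Protocol 7.10.3) | yes, where appropriate (10.8) | not named (7.1) |
| Vital signs | not needed here | not named in 10.8 | change named (7.4) |

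**2. Number of pairs**

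Inputs: about 126 randomized and 100 completing (SAP 2.2). Assumption: all 126 are dosed at Visit 3, 100 at Visit 4, and losses are equal by sequence. Sessions per product = 126/2 + 100/2 = 63 + 50 = 113. Taking one eye per subject gives n = 113 pairs per product.

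**3. Can new abnormalities be read from separate counts?**

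Let *a* eyes be abnormal before and *b* after. The number of eyes that went from normal to abnormal lies between max(0, b − a) and min(b, n − a). With n = 113 and assumed counts:

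| a (before) | b (after) | New abnormalities |
|---|---|---|
| 10 | 10 | 0 to 10 |
| 20 | 20 | 0 to 20 |
| 10 | 15 | 5 to 15 |
| 0 | 5 | exactly 5 |

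The bounds are the same at n = 100. Separate counts fix the number only in special cases, such as no abnormal eyes beforehand.

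**4. Can pressure rises be read from separate columns?**

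Assume an SD of 3 mmHg before and after, normally distributed values and no mean change. The SD of the individual change is 3 × √(2(1 − r)), where r is the pre/post correlation. The share of eyes rising by 5 mmHg or more is the normal upper tail beyond 5 divided by that SD:

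| r | SD of change (mmHg) | Share rising ≥ 5 mmHg |
|---|---|---|
| 0.3 | 3.55 | 7.9% |
| 0.6 | 2.68 | 3.1% |
| 0.9 | 1.34 | 0.01% |

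The two columns have the same mean and SD in all three rows. The 5 mmHg cut is illustrative only.

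**5. Which reference applies at Visit 4?**

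The wording of SAP 4.1 can be read in two ways. Read once per subject, the reference for both sessions is the examination before the Visit 3 dose, and a Visit 4 change would then span the washout of about two weeks. Read per treatment period, the reference is the examination before that session's dose. SAP 7.4 speaks of the first dose for vital signs; SAP 4.1 does not use that phrase, and nothing in the visible text settles the matter.

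**The case against.** The strongest reply has five parts.

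- **Adverse events.** A reader might infer that new ocular findings cannot be counted at all. The documents do not support that. The pairs are collected, and SAP 7.2 counts subjects with ocular treatment-emergent events by treatment, also by severity and relationship. What remains is narrower: under Protocol 9.1.1 an abnormal investigational finding becomes an adverse event only if it comes with signs or symptoms, leads to discontinuation of treatment, or is judged clinically relevant. Changes short of that have no table.
- **The protocol still stands.** SAP silence does not flatly contradict Protocol 10.8, and a safety baseline in SAP 4.1 suggests that some change was intended. This is fair. But the protocol wording is conditional, the SAP prevails, and 7.1 does not use the baseline. The intention should be written down.
- **SAP 4.1.** A reader might infer that it discards the Visit 4 pre-EEC examination. It is ambiguous, and that is all that can be said.
- **Visibility in the planned tables.** A reader might infer that a rise in a few eyes would be hidden. Not entirely: SAP 6.1 also reports SD, median, minimum and maximum. If five of 113 eyes rose by 8 mmHg, independently of their starting value, the mean would move by 5 × 8/113 = 0.35 mmHg. The SD would go from 3.0 to √(9 + 64 × (5/113) × (108/113)) = 3.4, and the maximum could move too. The tables would hint at a change without giving the number of eyes; the two maxima may also belong to different subjects. Nor is lost precision the issue. The SAP plans no pre-versus-post inference, and with complete pairs the difference in column means equals the mean change.
- **Pollen.** Within-session change includes the effect of the exposure, so it is not a drug effect by itself. This stands. The comparison to read is reproxalap against vehicle, and SAP 6.1 already provides the split: "Safety and efficacy will be summarized by treatment (Reproxalap 0.25%, Vehicle) where appropriate".

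The contents of SAP Table 2 and the Appendix are not visible in the text available. They might list such tables, so the point is made about the text of 7.1 only.

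**Conclusion.** The point holds in a limited form. SAP 7.1 plans separate pre- and post-EEC summaries for VA, SLE and NCT and leaves out the change or shift summary that Protocol 10.8 foresees. New or worsened findings below the adverse-event threshold are therefore not tabulated by product, although the paired data exist on both. The reference for Visit 4 needs one clarifying sentence.

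The size depends on how many eyes are already abnormal before dosing, which the documents do not give. With 10 or 20 abnormal eyes before and the same number after, the count of new abnormalities is uncertain over its whole range, 0 to 10 or 0 to 20. With none before, nothing is lost for SLE. All counts, the SD and the correlations above are assumptions; the conclusion that separate columns do not generally give the number of worsened eyes does not depend on their exact values.

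This is a gap in descriptive safety reporting. It does not affect the efficacy analysis, and nothing in the documents suggests that a safety signal is being concealed.

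**What to change.** In SAP 7.1 add, by product and by eye, within-session pre-to-post summaries for three tests:

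- **SLE:** a shift table with three grades (normal, abnormal not clinically significant, abnormal clinically significant).
- **VA:** the change, with the number of eyes worse and a statement of what counts as worse.
- **NCT:** a descriptive summary of the individual changes, including their minimum and maximum.

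State that for these three tests the reference is the pre-EEC examination of the same session, in place of the general rule in SAP 4.1. Add one sentence that within-session change includes the pollen exposure and is to be read as reproxalap versus vehicle. Descriptive statistics are enough; no confidence interval or test is needed.

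The cost is a few sentences in the SAP and a few extra descriptive tables. No data, visits or procedures are added.
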